6.3.2 Dose adjustments for QTcF prolongation

In case of QTcF >500 ms, (or QTcF prolongation >60 ms from baseline)

1. Assess the quality of the ECG recording and the QT value and repeat if needed
2. Interrupt study treatment
3. Determine the serum electrolyte levels (in particular hypokalemia, hypomagnesemia). If abnormal, correct abnormalities before resuming study drug treatment.
4. Review concomitant medication associated with QT prolongation, including drugs with a “Known”, “Possible”, or “Conditional risk of Torsades de Pointes”, and drugs with the potential to increase the risk of study drug exposure related QT prolongation
5. Check study drug dosing schedule and treatment compliance
6. Consider collecting a time-matched PK sample, and record time and date of last study drug intake.
7. Note that measurements of QTcF ≥ 480 ms shall be centrally verified on a copy of the original high quality recording that includes time and voltage scales

After confirming ECG reading at site, if QTcF > 500 ms

- Interrupt study treatment
- Repeat ECG and confirm ECG diagnosis by a cardiologist
- If QTcF confirmed > 500 ms:
 - Correct electrolytes, eliminate culprit concomitant treatments, and identify and address clinical conditions that could potentially prolong the QT
 - Consult with a cardiologist (or qualified specialist)
 - Increase cardiac monitoring as indicated, until the QTcF returns to ≤ 470 ms.
- After resolution to ≤ 470 ms, consider re-introducing treatment at reduced dose, and increase ECG monitoring for the next treatment(s):
 - If QTcF remains ≤ 500 ms after dose reduction, continue planned ECG monitoring during subsequent treatment
 - If QTcF recurs > 500 ms after dose reduction, discontinue patient from study drug.

6.3.3 Follow-up for toxicities

Please refer to IB for AEs of special interest.

6.3.3.1 Follow up on potential drug-induced liver injury (DILI) cases

Patients with transaminase increase combined with total bilirubin (TBIL) increase may be indicative of potential DILI, and should be considered as clinically important events.

The threshold for potential DILI may depend on the patient’s baseline AST/ALT and TBIL value; patients meeting any of the following criteria will require further follow-up as outlined below:

- For patients with normal ALT and AST and TBIL value at baseline: AST or ALT > 3.0 x ULN combined with TBIL > 2.0 x ULN

- For patients with elevated AST or ALT or TBIL value at baseline: [AST or ALT > 2 x baseline AND > 3.0 x ULN] OR [AST or ALT > 8.0 x ULN], combined with [TBIL > 2 x baseline AND > 2.0 x ULN]

Medical review needs to ensure that liver test elevations are not caused by cholestasis, defined as ALP elevation > 2.0 x ULN with R value < 2 in patients without bone metastasis, or elevation of ALP liver fraction in patients with bone metastasis.

Note: (The R value is calculated by dividing the ALT by the ALP, using multiples of the ULN for both values. It denotes whether the relative pattern of ALT and/or ALP elevation is due to cholestatic ($R \leq 2$), hepatocellular ($R \geq 5$), or mixed ($R > 2$ and < 5) liver injury).

In the absence of cholestasis, these patients should be immediately discontinued from study drug treatment, and repeat liver function testing (LFT) as soon as possible, preferably within 48 hours from the awareness of the abnormal results. The evaluation should include laboratory tests, detailed history, physical assessment and the possibility of liver metastasis or new liver lesions, obstructions/compressions, etc.

1. Laboratory tests should include ALT, AST, albumin, creatine kinase, total bilirubin, direct and indirect bilirubin, gamma-glutamyl transferase (GGT), prothrombin time (PT)/international normalized ratio (INR) and alkaline phosphatase.
2. A detailed history, including relevant information, such as review of ethanol, concomitant medications, herbal remedies, supplement consumption, history of any pre-existing liver conditions or risk factors, should be collected.
3. Further testing for acute hepatitis A, B, C or E infection and liver imaging (e.g. biliary tract) may be warranted.
4. Obtain PK sample, as close as possible to last dose of study drug, if PK analysis is performed in the study.
5. Additional testing for other hepatotropic viral infection (cytomegalovirus (CMV), Epstein-Barr virus (EBV) or herpes simplex virus (HSV)), autoimmune hepatitis or liver biopsy may be considered as clinically indicated or after consultation with specialist/hepatologist.

All cases confirmed on repeat testing meeting the laboratory criteria defined above, with no other alternative cause for LFT abnormalities identified should be considered as “medically significant”, thus, met the definition of SAE ([Section 8.2.1](#)) and reported as SAE using the term “potential drug-induced liver injury”. All events should be followed up with the outcome clearly documented.

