6.3 Dose modifications

6.3.1 Dose modification and dose delay

For patients who do not tolerate the protocol-specified dosing schedule, dose interruptions and/or reductions are either recommended or mandated in order to allow patients to continue the study treatment.

These dose modifications are summarized in [Table 6-2](#). Deviations to mandatory dose interruptions and/or reductions are not allowed. Permanent treatment discontinuation is mandatory for specific events indicated as such in [Table 6-2](#).

These dose changes must be recorded on the appropriate CRF.

Study drug (midostaurin/placebo)

[Table 6-2](#) describes toxicities (i.e., adverse drug reactions), laboratory values, or other assessments that require interruption or dose modification of study drug. Whether an AE that is not considered to be caused by the study treatment requires modifications needs to be assessed by the investigator. The need for modification in case of non-drug related AEs depends on the type of these AEs.

During induction and consolidation therapies, modifications must be done in case of non-hematologic toxicities, i.e., ADRs (pulmonary, cardiac or other non-hematologic toxicities).

During post-consolidation therapy, modifications must be done in case of hematologic and non-hematologic toxicities (pulmonary, cardiac or other non-hematologic toxicities).

If interruptions occur, missed doses of study drug will not be made up.

Study drug interruptions of greater than 28 consecutive days will require discontinuation from study treatment, unless the patient undergoes HSCT as in that case the drug interruption can be longer than 28 consecutive days (please refer to section 6.1.1 for more detailed information).

Cytarabine

Doses will be modified only during the consolidation phase with intermediate-dose cytarabine and in case of neurotoxicity, hematology and non-hematology toxicity. Please refer to [Table 6-2](#).

Idarubicin/ Daunorubicin

Doses will be modified during induction phase in case of hepatotoxicity, hematology and non-hematology toxicity. Please refer to [Table 6-2](#).

[figure not shown]
[figure not shown]
[figure not shown]

Table 6-2 Criteria for dose reduction/interruption and re-initiation of midostaurin/placebo, daunorubicin/idarubicin and cytarabine treatment for adverse drug reactions

[figure not shown]
Dose modifications for midostaurin/placebo	
Hematologic toxicities	

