During induction and consolidation cycles	No dose modifications are required for hematologic toxicity due to midostaurin/placebo during induction and consolidation therapy.
During post-consolidation cycles	In the presence of grade 4 neutropenia during post-consolidation therapy, midostaurin/placebo must be held until Absolute Neutrophil Count (ANC) $\geq 1.0 \times 10^9/L$. Once ANC $\geq 1.0 \times 10^9/L$, then resume midostaurin/placebo at the previous dose. If neutropenia persists for more than two weeks, then discontinue midostaurin/placebo protocol therapy.
Non-Hematologic toxicities:	

 Pulmonary toxicities 	
During induction, consolidation and post-consolidation cycles	For \geq grade 3 pulmonary infiltrate , midostaurin/placebo must be interrupted for the remainder of the cycle. Resume midostaurin/placebo at the same dose when infiltrate resolves to \leq grade 1. Missed doses of midostaurin/placebo will not be made up. If there is no improvement after 28 days, the patient must be discontinued from study drug.

 Cardiac Toxicity 	
During induction, consolidation and post-consolidation cycles	
 For QTcF interval > 470 ms and ≤ 500 ms, check magnesium and potassium levels and correct any abnormalities. If possible, stop any medications that may prolong the QTcF interval. Decrease midostaurin/placebo to 50 mg once daily for the remainder of the cycle. Resume midostaurin/placebo at the initial dose in the next cycle provided that QTcF interval improves to ≤ 470 ms at the start of that cycle. Otherwise continue midostaurin/placebo 50 mg once daily. For QTcF interval > 500 ms and/or QTcF prolongation >60 ms from baseline, check magnesium and potassium levels and correct any abnormalities. Hold or interrupt midostaurin/placebo for the remainder of the cycle, and, if possible, stop any medications that may prolong the QTcF interval. If QTcF improves to ≤ 470 ms just prior to the next cycle, resume midostaurin/placebo at the initial dose. If QTcF interval is not improved to ≤ 470 ms in time to start the next cycle, midostaurin/placebo may be held up to 28 days. If there is no improvement after 28 days, the patient must be discontinued from study drug.

 Other Non-Hematologic toxicity 	

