
During induction and consolidation cycles
 
During post-consolidation cycles
	
 • Grade 1/2: No dose modifications for any grade 1 or 2 non-hematologic toxicity. • Grade 3/4: If a patient experiences other grade 3/4 non-hematologic toxicity considered related to midostaurin/placebo, midostaurin/placebo will be interrupted until toxicity resolves to \leq grade 1. If the toxicity resolves prior to day 21, then restart at same dose to complete current cycle. Missed doses of midostaurin/placebo will not be made up. A study drug interruption in excess of 28 days will require discontinuation of study treatment. • Grade 1/2: Persistent grade 1 or 2 toxicity during post-consolidation therapy that patients deem to be unacceptable may prompt a study drug interruption for as long as 28 days. A study drug interruption in excess of 28 days will require discontinuation of study treatment. • Grade 3/4: For other grade 3/4 non-hematologic toxicities that are considered to be related to midostaurin/placebo, interrupt midostaurin/placebo. Resume midostaurin/placebo at the same dose when toxicity resolves to \leq grade 2. If midostaurin/placebo is held for more than 28 days, then discontinue midostaurin/placebo post-consolidation therapy.

Dose modifications for intermediate-dose cytarabine (IDAC) induction 2 if applicable and consolidation therapy
	

During Induction 2 if applicable and consolidation cycles
	
Dose reduction according to institutional guidelines except in case of neurotoxicity dose modifications as below: Contributions of concomitant medications to neurotoxicity should be assessed and other medications discontinued if possible.
 
For neurotoxicity \geq grade 2 due to intermediate-dose cytarabine, discontinue cytarabine for the remainder of the cycle. Intermediate-dose cytarabine may be considered at the next consolidation therapy cycle with a dose modification from 1500mg/m² to 1000mg in patients <60 years of age and from 1000mg/m² to 600mg/m² in patients \geq60 of age if the toxicity has resolved to \leq grade 1.
 
For a second occurrence of neurotoxicity \geq grade 2, intermediate-dose cytarabine should be permanently discontinued.

Dose modifications for daunorubicin		
	Dose reduction according to institutional guidelines except in case of hepatotoxicity dose modifications as below:	
During induction cycles	Total Bilirubin (mg/dL)	% daunorubicin dose to administer
	≤ 1.2	100%

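### For a related grade 3/4 liver event that meets the potential-DILI criteria, Table 6-2 allows a same-dose restart of study drug while Protocol 6.3.3.1 orders discontinuation

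*Protocol*

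**What the plan says.** **Section 6.3.3.1.** The criteria are laboratory-based. With normal baseline values they are AST or ALT above 3 x ULN together with TBIL above 2 x ULN. With abnormal baseline values the thresholds are partly relative to baseline. Medical review must rule out cholestasis. The instruction is then: "In the absence of cholestasis, these patients should be immediately discontinued from study drug treatment". Repeat testing and a work-up follow, and confirmed cases with no other cause are reported as SAEs. No route back to study drug is described.

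**Section 6.3.1.** Table 6-2 is introduced as describing toxicities, "laboratory values, or other assessments that require interruption or dose modification of study drug". The section also states: "Permanent treatment discontinuation is mandatory for specific events indicated as such in" Table 6-2.

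**Table 6-2, midostaurin/placebo part.** The entries are hematologic, pulmonary, cardiac and other non-hematologic. None mentions liver, transaminases, bilirubin, DILI or 6.3.3.1. For related grade 3/4 events, the other non-hematologic row interrupts study drug until grade 1 or lower in induction and consolidation, and adds: "If the toxicity resolves prior to day 21, then restart at same dose to complete current cycle". In post-consolidation it says: "Resume midostaurin/placebo at the same dose when toxicity resolves to" grade 2 or lower. Its only trigger for discontinuation is a hold longer than 28 days.

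**Table 6-2, chemotherapy parts.** The table's hepatic instructions are here. The daunorubicin entry reads "Dose reduction according to institutional guidelines except in case of hepatotoxicity dose modifications as below", followed by a bilirubin scale. The idarubicin entry also has a bilirubin limit.

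**Sections 7.1.4 and 6.1.4.** Section 7.1.4 makes discontinuation compulsory in circumstances set out in Section 6.3. Section 6.1.4, on continuing treatment, refers the reader to Section 6.3 as a whole.

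**The concern.** A site that doses from Table 6-2 finds no liver entry for study drug and falls through to the residual row. That row is not silent on a related grade 3/4 liver event. It gives an instruction, and for a potential-DILI case without cholestasis the instruction is the wrong one: restart at full dose after resolution.

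The layout makes this slip possible. The stop order sits under a heading about following up toxicities, and the visit schedule (Table 7-1) cites 6.3.3.1 for hepatic tests, not for dosing.

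What is at stake is re-exposure to study drug of a patient whom the protocol takes off it for possible liver injury. Some liver signal is foreseeable: Section 1.2.1.2 reports that transaminase elevations were more frequent on midostaurin in A2301. SAP 9.3 plans to count patients with ALT or AST above 3 x ULN and TBIL above 2 x ULN.

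**Working it through.** The check is a comparison of texts. The plan states no figure on this point, so there is nothing to reproduce.

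| | Section 6.3.3.1 | Table 6-2, other non-hematologic row |
|---|---|---|
| Trigger | AST/ALT and TBIL criteria, no cholestasis | Grade 3/4, judged related to midostaurin/placebo |
| Grade or relatedness needed? | No | Both |
| First action | Discontinue at once | Interrupt |
| Restart, induction/consolidation | None given | Same dose, if resolved to grade 1 or lower before day 21 |
| Restart, post-consolidation | None given | Same dose, at grade 2 or lower |
| Permanent stop | Immediate | Only if the hold exceeds 28 days |

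1. *Same first step.* Both texts stop the drug immediately. They part only on what follows.

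2. *What discontinuation means.* The glossary defines study treatment discontinuation as permanent. It defines the term for study treatment, whereas 6.3.3.1 speaks of study drug, but nothing in 6.3.3.1 suggests a temporary hold.

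3. *Where the texts overlap.* An event must satisfy both triggers: related, grade 3/4, both laboratory criteria met, no cholestasis. An isolated grade 3/4 transaminase rise without the bilirubin criterion is outside 6.3.3.1, so a same-dose restart there contradicts nothing.

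4. *A case in the overlap.* Take a post-consolidation patient with normal baseline liver tests who meets both laboratory criteria, has no cholestasis, and whose event is judged related and graded 3 (the grade is an assumption for illustration). Under 6.3.3.1 study drug ends. Under the residual row it is held and then resumed at the same dose, which for a patient on the planned dose is 50 mg twice daily, once the event is grade 2 or lower within 28 days.

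5. *How wide the explicit restart is in induction and consolidation.* Study drug starts on day 8 in induction 1 and on day 4 in induction 2 and consolidation (Section 6.1.1.1). The last day before day 21 is day 20. For a toxicity arising on study drug within the cycle, onset and resolution to grade 1 or lower must both fall within 20 − 8 + 1 = 13 days, or 20 − 4 + 1 = 17 days. For later resolution the row ends the hold but states no restart dose. The post-consolidation instruction has no day limit other than the 28-day maximum hold.

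6. *Which text governs.* Section 7.1.4 uses compulsory wording and covers circumstances in Section 6.3, which contains 6.3.3.1. A reader who follows the whole protocol should discontinue.

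**The case against.** The strongest reply is that the protocol already resolves this. Section 7.1.4 compels discontinuation, Section 6.1.4 sends the reader to all of 6.3, and 6.3.3.1 follows the table closely. Section 6.3.1 makes discontinuation mandatory for events marked in the table; it does not say that only those events count. A specific rule should override a residual one, and once the drug is discontinued a restart clause has nothing to act on. Confirmed cases without another cause are SAEs, reportable within 24 hours (Section 8.2.2), so the sponsor would learn of them.

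Most of this stands, and it limits the point to a minor one. It does not remove it. The residual row has no liver exception and prescribes an action that 6.3.3.1 excludes. Precedence has to be worked out from another chapter, and SAE reporting does not tell the site what to do with the drug.

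Three stronger readings are tempting but unsupported:

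- *That the protocol has no DILI stopping rule.* It has one, and it is binding.
- *That QTcF shows how a stop rule should be carried in both places.* The Table 6-2 row says "Hold or interrupt midostaurin/placebo for the remainder of the cycle", resumes at the initial dose and stops the drug after 28 days without improvement. Section 6.3.2 considers re-introduction at a reduced dose and says to "discontinue patient from study drug" if QTcF exceeds 500 ms again after that reduction. The row does not carry the subsection's own stop rule, so it is no model.
- *That the grade 1/2 branch, which makes no dose change in induction and consolidation, also conflicts.* That depends on CTCAE liver cut-offs that the documents do not print.

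**Conclusion.** The inconsistency is real and narrow. For events that are related, grade 3/4 and meet the 6.3.3.1 criteria without cholestasis, Table 6-2 instructs a same-dose restart after resolution where 6.3.3.1 requires that study drug be discontinued. The second text should prevail. This is a minor patient-safety inconsistency in the dosing table, with no bearing on power, type I error or the EFS analysis.

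Its frequency cannot be stated. The A2301 remark concerns transaminases only, and no rate of combined AST/ALT and bilirubin elevation is given. That the residual row applies in every treatment phase describes its scope and says nothing about how often the conflict would arise.

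The conclusion assumes that discontinuation in 6.3.3.1 is permanent, as the glossary definition and the absence of a restart rule both indicate. It concerns the plan as written. The SAP records that the study was stopped for futility, with some patients continuing treatment, and nothing in the documents shows that any patient was restarted wrongly.

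**What to change.** Add a row to the midostaurin/placebo part of Table 6-2 along these lines: Potential DILI: discontinue study drug per 6.3.3.1. Add one sentence stating that these cases are excluded from the restart instructions in the other non-hematologic row.

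The cost is one row and one sentence, by amendment. No tests, visits or analyses are added: the work-up is already in 6.3.3.1, the visit schedule already cites it for hepatic tests, and the SAP already tabulates the combined liver category. Because the trial has been stopped, the practical value now lies mainly in any protocol that reuses this table.

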6.4 Concomitant medications

Administration of certain concomitant medications may lead to the requirement for subject to be discontinued. Such cases should be discussed with the sponsor on a case by case basis.

6.4.1 Permitted concomitant therapy

Supportive therapy including prophylactic antibiotic and antifungal treatments, transfusions, growth factors etc. will be administered at the discretion of the investigators according to standard of care.

The patient must be told to notify the investigational site about any new medications he/she takes after the start of the study drug. All medications (other than study drug) and significant non-drug therapies (including physical therapy, herbal/natural medications and blood transfusions) administered during the study must be listed on the Prior or Concomitant non-drug therapies/procedures CRF.

6.4.2 Permitted concomitant therapy requiring caution and/or action

Strong CYP3A4 inhibitors should be used with caution due to potential increase in midostaurin exposure. Alternative medicinal products that do not strongly inhibit CYP3A4 activity should be considered. In situations where satisfactory therapeutic alternatives do not exist, patients should be closely monitored for midostaurin-related toxicity.

Based on in vitro data, midostaurin and its active metabolites may have the potential to inhibit P-glycoprotein (P-gp), BCRP, and OATP1B1. Midostaurin, CGP62221 and CGP52421 can potentially induce the following CYPs: CYP1A2, CYP2B6, CYP2C8, CYP2C9, CYP2C19, CYP3A4 and inhibit the following ones: CYP1A2, CYP2C8, CYP2C9, CYP2D6, CYP2E1, CYP3A4/5. In absence of clinical data medicinal products with a narrow therapeutic range that are substrates of these CYPs should be used with caution when administered concomitantly with midostaurin, and may need dose adjustment to maintain optimal exposure.

Therefore medicinal products with a narrow therapeutic range that are substrates of CYP1A2, CYP2B6, CYP2C8, CYP2C9, CYP2D6, CYP2E1, CYP3A4/5, P-gp, BCRP or OATP1B1 should be used with caution when administered concomitantly with midostaurin and may need dose adjustment to maintain optimal exposure.

A list of strong CYP3A4 inhibitors, substrates with narrow therapeutic index for CYP1A2, CYP2B6, CYP2C8, CYP2C9, CYP2C19, CYP2D6, CYP2E1, CYP3A and P-gp and substrates of BCRP and OATP1B1 is available in [Appendix 1](#).

6.4.3 Prohibited concomitant therapy

Strong CYP3A4 inducers: Concomitant use of midostaurin/placebo with strong inducers of CYP3A4 should be avoided. Strong CYP3A4 inducers decrease exposure of midostaurin and its active metabolites (CGP52421 and CGP62221). In a study in healthy subjects, coadministration of the strong CYP3A4 inducer rifampicin (rifampin, 600 mg daily) to steady state with a single dose of midostaurin decreased midostaurin C_{max} by 73% and -AUC_{inf} by 96% in average, respectively. CGP62221 exhibited a similar pattern. The mean AUC_{last} of CGP52421 decreased by 60%. In absence of clinical data, the impact of strong CYP3A4 inducers on midostaurin exposure at steady-state was investigated based on physiologically-based PK models. Exposure was predicted to be decreased by 60%.

A list of strong inducers of CYP3A4 is available in [Appendix 1](#).

Other prohibited concomitant medications: If concomitant administration of drugs with a “known risk of torsades de pointes (TdP)” is required and cannot be avoided, then the study drug must be interrupted. If, based on the investigator assessment and clinical need, study treatment is resumed, close ECG monitoring is advised. Note that measurements of QTc_≥480ms shall be centrally verified on a copy of a high quality recording that includes time and voltage scales.

If during the course of the study, concomitant administration of a drug with “Possible risk of TdP” or “Conditional risk of TdP” is required, based on the investigator assessment and clinical need, study treatment may be continued with close ECG monitoring to ensure patient safety. A list of drugs associated with QT prolongation and/or TdP is available online at [www.qtdrugs.org].

As far as possible avoid co-administering drugs with a “Known”, “Possible”, or “Conditional” risk of TdP during the course of the study:

- If concomitant administration of drugs with a “Known risk of TdP” is required and cannot be avoided, study drug must be interrupted. If, based on the investigator assessment and clinical need, study treatment is resumed, close ECG monitoring is advised.
- If during the course of the study, concomitant administration of a drug with “Possible risk” or “Conditional risk of TdP” is required, based on the investigator assessment and clinical need, study treatment may be continued under close ECG monitoring to ensure patient safety.

A list of drugs associated with QT prolongation and/or TdP is available online at [www.qtdrugs.org]

